### 7.2. Regulatory Status of Drug

Both desogestrel and the COCP have marketing authorisation in the UK, but their use in this trial is outside the indications listed on the Summary of Product Characteristics (SmPC's) and therefore outside of their respective marketing authorisation.

### 7.3. Product Characteristics

The product characteristics for each treatment is listed within the relevant SmPC. Section 4 provides information on the clinical particulars of each treatment. The reference safety information is detailed in section 4.8.

Known drug interactions are listed in section 7.8 of the protocol.

### 7.4. Drug Storage and Supply

All IMP stock will be managed via the trial REDCap database. IMP will be delivered directly to site from the IMP supplier on behalf on the NCTU, following instruction from a member of the DEBi trial team. IMP will be delivered in batches of individually sealed boxes, identifiable only with the batch number and IMP pack code. On delivery IMP should be stored below 25°C in accordance with the

instructions on the IMP label following local processes (e.g. clinic onsite storage, pharmacy storage etc).

The initial bulk shipment of IMP will be ordered once the site greenlight checklist has been completed. IMP is required to be onsite, with receipt of IMP confirmed, prior to the start of recruitment. The trial database will notify the NCTU trial team when individual sites require additional stock. The NCTU will liaise with both the site and IMP supplier when resupplying sites with batches of IMP.

Sites will not be required to return unused IMP back to the NCTU, Sponsor or IMP supplier. Expired stock can be destroyed in accordance with local processes. Once all trial recruitment and follow-up has concluded, unused stock can be destroyed. If the site closes early, with in date but unused stock, the site should contact the NCTU to confirm whether the stock can be destroyed.

Participants who require replacement IMP (e.g. lose trial supply etc) can be resupplied their allocated treatment via REDCap. The NCTU can be contacted should replacement IMP be required.

All participants will be provided with a copy of the current version of the DEBi Participant Information Leaflet when dispensed their trial treatment. This provides them with information on the medicine, including possible side effects and storage conditions.

If IMP recall is required at any point during the trial, the site will be notified of this by the NCTU and provided with guidance on identifying affected stocks and how to manage the recall process at the site. The current version of the DEBi IMP guidelines will include information on contacts for IMP supplier and NCTU as well as guidance on the processes outlined above (e.g. ordering IMP through REDCap).

### 7.5. Preparation and Labelling of IMP

In accordance with the MHRA risk-adapted approach to the management of Clinical Trials of Investigational Medicinal Products (CTIMPs) DEBi is categorised as a medium risk Type B trial as the IMPs are being used outside their licenced indication. As the trial is blinded, all trial medications will be supplied by NCTU and will be delivered to recruiting sites and/or pharmacies by a third-party supplier in blinded packaging with Annex 13 compliant labelling (in line with paragraph 32, which remains applicable until UK legislation replaces it). Site staff will not be required to make any modifications to the IMPs prior to dispensing. More detailed information on IMP handling and management can be found in the current version of the trial IMP guidelines.

### 7.6. Dosing Schedules

Both trial treatments desogestrel 75mcg and COCP (levonorgestrel 150mcg/ethinylestradiol 30mcg) are to be taken orally, once a day, at the same time each day for the 90-day duration of a persons participation in the trial.

In the case of any missed doses, participants will be advised to take the dose as soon as they have remembered if less than 24 hours late. If a dose is more than 24 hours late the dose should be disregarded and the next dose taken. Participants will be asked to confirm they have taken their pill when they complete the daily bleeding diary. No participant will be removed from the trial for non-adherence to treatment schedule.

### 7.7. Dose Modifications

Dose modifications are not permitted on the trial. Should the participant experience a suspected adverse reaction to the treatment, the treatment should be stopped immediately in line with guidance from their clinical care team.

### 7.8. Known Drug Interactions and other Therapies

Liver enzyme inducing medicines which induce the cytochrome CYP3A4 should not be co-administered for 6 weeks prior to recruitment onto the trial, commencement of the trial treatment or any time during the 90-day trial participation. Liver enzyme inducing medications will reduce the plasma concentration of both desogestrel and COCP. To check for drug interactions please visit <https://bnf.nice.org.uk/interactions/>.

Treatments include but are not limited to:

- Antibiotics – rifampicin and rifabutin
- Antiseizure medications- carbamazepine, eslicarbazepine acetate, oxcarbazepine, perampanel, phenobarbital, phenytoin, primidone, rufinamide, topiramate.
- Antiretrovirals – ritonavir, efavirenz and nevirapine
- St John’s Wort
- Lamotrigine

Further details can be found in section 4.5 of the SmPCs.

### 7.9. Concomitant Medications

The following concomitant use or use within the last 3 months of hormones (except DMPA) or medications known to affect menstrual bleeding, including progestogens, estrogens, androgens, tranexamic acid, routine use of oral NSAIDs, anticoagulants, selective progestogen receptor modulators **are not** permitted. Current use or use within the last 6 months of gonadotrophin-releasing hormone analogues and 9 months of DMPA is not permitted.

A full list of concomitant medications can be found in appendix Table 12-Concomitant medications Table 12-Concomitant medications.

Other medication (not included in Table 12) is permitted but should be recorded at baseline or self-reported by participant if started during participation in the trial.

The following medications do not need recording/self-reporting: paracetamol, proton pump inhibitors, vitamins, opioids, H1 receptor antagonists (e.g. cyclizine, loratadine, chlorphenamine), H2 receptor antagonists (e.g. ranitidine), laxatives (osmotic or stimulant), anti-depressants – selective serotonin re-uptake inhibitors or tricyclic or venlafaxine, inhaled or topical corticosteroids, insulin, biguanides e.g. metformin, anti-fungal drugs, emollients, iron, anti-emetics – dopamine D2 receptor antagonists e.g. metoclopramide, domperidone, anti-psychotics (1st or 2nd generation), loperamide, aciclovir, nicotine.

### 7.10. Trial Restrictions

Potential participants will have their eligibility assessed prior to recruitment in the trial, this includes a review of potential contraindications to both treatments as per exclusion criteria section 4.2

There are no additional trial specific restrictions. All sites will be provided with an information card to share with randomised participants with details on the trial and the two treatments that the participant may have been allocated. It is at the investigator or delegates discretion as to whether they provide the cards to participants in addition to the GP notification.

### 7.11. Assessment of compliance with Treatment

Participants will be asked to complete a daily bleed and medicine adherence diary which will include a question as to whether they have taken their pill. Participants will be prompted (MyCap, email or text message) to complete missing data for 5 days following the scheduled data collection point. Where a participant has multiple episodes of treatment non-compliance on self-reporting, either the NCTU and/or the recruiting site will contact the participant to provide support and to confirm the information is correct and to ascertain the reason for not treatment non-compliance, as well as a welfare check to determine if there are any Serious Adverse Events (SAEs) leading to compliance challenges as per the current trial monitoring plan.

Participants will be asked to return their blister packs to their recruiting clinic at the end of their participation so that self-reported adherence can be confirmed. It is acknowledged that a limitation of this is that participants may have thrown the empty blister packs away.

### 7.12. Name and description of each Non-IMP

There are no Non-Investigational Medicinal Products in the trial.

## 8. Trial procedures and assessments

### 8.1. Summary of assessments

**Table 7-Trial Assessments**

Activity	Timepoint				
	Baseline	Randomisation	Follow-up (days)		
			30	60	90
Informed consent	X				
Baseline demographic data	X				
Perception of bleeding pattern			X	X	X
Bleeding status	X (recall over previous 90 days)			Once daily	
Randomisation		X			
Intervention: Desogestrel or COCP				Once daily	
Health Related Quality of life (EQ-5D-5L)	X		X	X	X
Capacity-wellbeing (ICECAP-A)	X		X	X	X
Acceptability			X	X	X
Global impression of treatment					X
Adverse effects of treatment			X	X	X
Adherence to treatment				Once daily	
Adherence to treatment return of blister packs					At the end of individual participation in the trial
Healthcare resource use	X		X	X	X
Gratitude voucher			X	X	X

Intention to continue treatment					X
---------------------------------	--	--	--	--	---

**8.2. Trial Procedures and Schedule of Assessments**

**8.2.1. Baseline Visit**

Screening data for patients entering the trial will be collected by each site and recorded within the trial database.

**8.2.2. Informed consent**

Informed consent will be obtained as described in section 5.2.

**8.2.3. Baseline data collection**

After informed consent and eligibility assessments are complete, baseline visit data will be collected. This will include participant demographic, baseline questionnaire data and bleeding status information. The full list of baseline data collected for this trial is listed in the current version of the Data Management Plan (DMP).

**8.2.4. Routine assessments and eligibility**

Patients who attend a consultation for problem bleeding whilst using the implant will be examined to exclude other possible causes of bleeding as part of standard care. This will include an assessment of drug interactions, a speculum examination to assess the cervix for pathological causes of bleeding, a high sensitivity urine pregnancy test and Sexually Transmitted Infections (STI) screen for gonorrhoea and chlamydia. These will be performed by the clinic staff in line with standard practice.

Any potential participant who declines a pregnancy test or speculum examination will not be able to participate in the trial because some exclusion criteria cannot be verified. The STI results will be available in approximately 5 working days. Those requiring pelvic ultrasound and/or hysteroscopy cannot be enrolled at the first trial visit.

Once other causes have been excluded, they will be introduced to the trial and if interested provided with the trial PIS and asked to sign informed consent. Following consent, the patient will be assessed for eligibility and baseline data collected. Eligibility will be confirmed and signed off by the principal investigator (or delegated trial clinician as per section 4.3) on the eligibility checklist form once informed consent and baseline data have been obtained. This must be completed prior to randomisation.

Those who do not meet eligibility criteria will have the reason explained to them and that it will not impact on their care. They will then continue to have routine care without delay.

**8.2.5. Randomisation**

Participants will be randomised to receive either desogestrel or COCP using a minimisation algorithm implemented in REDCap. Randomisation will be performed by a suitably delegated member of the recruiting site research team. As the trial is blinded, neither the participant nor the recruiting site staff will know which of the two treatments the participant has received.

There is a small chance that, at the end of the trial when stock is being run-down, only one of the trial IMPs will be available and the minimisation algorithm will be constrained to allocate to the

WPD 3.1\_Protocol Template\_Version 3.1\_20-Apr-2023

Document Title:	Protocol
Trial Name:	DEBI
Version No:	Final 2.0
Version Date:	06Jun2025

available IMP. However, the chance of this occurring will be minimised by constantly monitoring the IMP stock levels. If stock is not available for more than two weeks during the trial, the trial management may consider pausing the randomisation within the affected sites until after stock levels are back to normal to avoid any imbalance in treatment allocation.

#### 8.2.6. IMP dispensing

An IMP pack code, assigned to the correct treatment arm will be linked to the participant at the point of randomisation to allow the recruiting site to dispense the allocated IMP to the participant. Participants will be dispensed their entire 90-day course of IMP at randomisation, in line with the treatment they would receive as part of routine clinical practice.

Participants will be advised to start their treatment **the day after** their clinic visit and randomisation.

#### 8.2.7. Follow-up procedures

In accordance with standard clinical practice, participants will not be required to revisit their sexual health service or GP as part of their participation in this trial. Following randomisation, the majority of follow-up information will be obtained directly from the participants (via questionnaires) and coordinated by the NCTU without further involvement from the recruiting site. Following the participant's completion of the trial, the site staff will be asked to reveal the treatment allocation to the participant (either as part of their 3-month standard care visit or via telephone call), confirm the participant's adherence to treatment (where possible) and confirm whether the participant intends to continue on their allocated treatment to manage their problem bleeding. Follow-up timepoints for the trial are detailed in Figure 2-Routine clinical assessment outcome flowchart.

#### 8.2.8. Daily bleeding status

Follow-up of participants will start the day after randomisation and will continue for the duration of their 90-day participation. Participants will be asked to complete a daily bleeding diary (MyCap or paper) recording their bleeding status in the previous 24hr period. Diaries need to be completed daily, with a tolerance window of 5 days to allow for retrospective completion where a day has been missed.

#### 8.2.9. Treatment adherence

Participants will be asked daily (MyCap or paper) if they had taken their pill the previous day at the same time as they are asked about their bleeding status in the previous 24hrs.

Participants will be asked to save all treatment blister packs, for these to be returned to the recruiting clinic and adherence to be reviewed by a member of the clinical team. Participants will be asked to return these to their recruiting clinic during their 3-month standard care review, and where this does not take place the trial research team will facilitate the return of the blister packs.

#### 8.2.10. 30- and 60-day Follow-up Questionnaires

Participants will complete a questionnaire (online, postal or telephone) at 30 and 60 days after randomisation which will collect information on the following:

- Bleeding days and episodes
- Perception of their bleeding pattern
- Treatment acceptability
- Reporting of symptoms and known treatment side effects
- Medications

- Use of health service resources relating to problem bleeding or contraceptive use
- Out of pocket expenses for treatments or products in relation to problem bleeding
- Health Related Quality of life (EQ-5D-5L)
- Capacity-wellbeing (ICECAP-A)
- Removal of implant

### 8.2.11. 90-day Follow-up Questionnaires

Participants will complete a questionnaire (online, postal or telephone) at 90 days after randomisation which will collect information on the following:

- Bleeding days and episodes
- Perception of their bleeding pattern
- Treatment acceptability
- Global impression of treatment
- Reporting of symptoms and known treatment side effects
- Medications
- Use of health service resources relating to problem bleeding or contraceptive use
- Out of pocket expenses for treatments or products in relation to problem bleeding
- Health Related Quality of life (EQ-5D-5L)
- Capacity-wellbeing (ICECAP-A)
- Intention to continue using implant and allocated trial treatment

At the end of the 90-day participation period, participants will be unblinded to their treatment allocation by their recruiting site. Unblinding will take place at the 3-month standard care visit, or for participants who are unable/unwilling to attend a clinic visit, the recruiting centre will call the participant to reveal their treatment allocation over the telephone. The recruiting centre will be asked to confirm whether the participant intends to continue with their implant and allocated trial treatment (as part of their standard care) once their participation in the trial has concluded.

Completion windows for 30-, 60- and 90-day questionnaires will be 10 days. Questionnaires will no longer be available for completion once outside of the specified completion window; therefore, no protocol deviations will be required for completion of data outside of the specified data collection windows.

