	
Participant-reported resolution of problem bleeding, with resolution defined as self-reported significant improvement in the bleeding pattern during the 90-day reference period. Improvement in problem bleeding will be measured by participants' self-determination that their bleeding pattern has improved using a 5-point Likert scale.
 
Secondary outcomes
 
Clinical effectiveness
 
 
• Longest duration of consecutive non-bleeding (no bleeding or spotting) whole days for each 30-day period within the 90 days.
 
• Total number of non-bleeding, spotting and bleeding days during the 90-day treatment period
 
• Number and duration of bleeding episodes (one or more consecutive days of bleeding, bounded by bleed-free days) within the 90 days
 
• Time to the longest consecutive non-bleeding days
 
 
Treatment acceptability and adherence
 
 
• Acceptability of treatment (side effects)
 
• Adherence to treatment
 
 
Safety
 
 
• Discontinuation of allocated treatment and of implant
 
 
Cost-effectiveness
 
 
• Quality of life (EQ-5D-5L and ICECAP-A)
 
• Primary care, sexual health, and secondary care health resource use
 
• Personal and out of pocket expenses arising from problem bleeding
 
• Intention to continue the trial drug at 3 months
 

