### 2.3. Secondary Objectives and Outcome Measures

**Table 2-Secondary Objectives**

Objective	Outcome Measure	Time Point	Method of Collection
To establish if the proportion of participants reporting problem bleeding is not worse in participants treated with desogestrel compared to COCP.	Participant self-reported significant improvement in the bleeding pattern.	Day 30 and 60	Participant Questionnaire
	Longest duration of consecutive non-bleeding (no bleeding or spotting) whole	Daily	Daily bleeding diary

	days for each 30-day period within the 90 days.		
To determine the effect of desogestrel compared with COCP on total number of non-bleeding, spotting and bleeding days during the 90-day treatment period	Participant self-reported bleeding pattern.	Daily	Daily bleeding diary
To determine the effect of desogestrel compared with COCP on the number and duration of bleeding episodes (one or more consecutive days of bleeding, bounded by bleed-free days) within the 90 days	Participant self-reported bleeding pattern.	Daily	Daily bleeding diary
To determine the effect of desogestrel compared with COCP on the time to the longest consecutive non-bleeding days	Participant self-reported bleeding pattern.	Daily	Daily bleeding diary
To determine the acceptability with trial treatment	Participant-reported side effects	Day 30, 60 and 90	Participant Questionnaire
To establish participant adherence to treatment	Participant reported adherence to trial treatment	Daily	Daily bleeding diary
	Participant reported discontinuation/removal of their implant	Day 30, 60 and 90	Participant Questionnaire
To determine the effect of desogestrel and COCP on participant Quality of life	Participant reported EQ-5D-5L and ICECAP-A	Day 30, 60 and 90	Participant Questionnaire

WPD 3.1\_Protocol Template\_Version 3.1\_20-Apr-2023

To determine the cost of treating implant user problem bleeding with desogestrel or the COCP	Treatment and healthcare usage	Day 30, 60 and 90	Participant Questionnaire
To determine the proportion of participants who intend to continue their allocated treatment.	Participant reported	Day 90 or sooner if early withdrawal from trial	Participant Questionnaire

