**Table 8-Withdrawal type and procedure post randomisation**

Withdrawal type	Withdrawal procedure	Use of data
Withdrawal from trial treatment	Any participant that requests to discontinue trial treatment will be marked as withdrawn from treatment on the trial database but will be asked to continue to complete questionnaires if willing. Information on reason for stopping trial treatment will be recorded by the site if given, and patient care will continue as part of standard clinical practice.	Any data collected prior to participant withdrawal will be retained and used in the analysis.
Removal of implant	Any participant who notifies the trial or site team that their implant has been removed during their participation in the trial would be withdrawn from the trial and unblinded to their treatment allocation to	Any data collected prior to participant withdrawal will be retained and used in the analysis.

	inform their ongoing contraceptive care. Participants would not be required to complete any further questionnaires or daily diaries but would be followed up for safety outcomes for 7 days following stopping of their trial treatment.	
Withdrawal from daily bleed diary	Any participant that requests to discontinue from daily bleed diary will be marked as withdrawn from diary collection on the trial database and no further MyCap notifications will be sent. Withdrawal from the daily diary does not withdraw from questionnaire completion.	Any data collected prior to participant withdrawal will be retained and used in the analysis.
Withdrawal from follow up questionnaires	Any participant that requests to discontinue from trial questionnaires will be marked as withdrawn from questionnaire collection on the trial database and no further contact relating to questionnaires will be made. Withdrawal from questionnaires does not withdraw from daily diary completion.	Any data collected prior to participant withdrawal will be retained and used in the analysis.
Withdrawal from long-term follow-up	Any participant that withdraws consent for the long term follow-up will be recorded within the database and no long term follow-up data will be collected.	Any data collected prior to participant withdrawal will be retained and used in the analysis.

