##### 14.2.2. Secondary outcomes

**Table 10-Secondary outcomes**

Outcome Measure	Definition or derivation
Participant's self-reported significant improvement in the bleeding pattern.	At day 30, 60 and 90 as for primary outcome

Participant's self-reported non-worsening of the bleeding pattern	The 5-point Likert scale will be dichotomised into a response of "improved significantly" or "improved slightly" or "no change" versus "worsened slightly" or "worsened significantly"
Participant self-reported bleeding pattern.	Total number of days, within the 90-day window, of: 
 
- no bleeding
 
- spotting
 
- bleeding
 

Longest duration of consecutive non-bleeding (no bleeding or spotting) whole days for each 30-day period within the 90 days.	Longest consecutive number of days with responses of no bleeding or spotting, in 90 days
Time to longest episode of consecutive non-bleeding whole days	Time to the first day of the longest consecutive number of days with responses of no bleeding or spotting, over the 90 days.
Number of bleeding episodes	Number of episodes with one or more consecutive days of reported bleeding, bounded by bleed-free days, within the 90 days
Duration of bleeding episodes	Number of episodes of 2, 3 (etc, to maximum reported) consecutive days with reported bleeding.
Participant-reported side effects	Measured at baseline and day 30, 60 and 90 to assess whether a participant has experienced the side effect and if so the extent of the side effects so that they can be compared to previous timepoints. (Using no/yes "mild", "moderate" or "severe"
Participant reported adherence to trial treatment	Responses will be categorised as all (90/90 pills), most (63-89/90), some (36-62/90), few (1-35/90) and none (0/90). 'Few' and 'None' categories would be classed as treatment non-adherence.
Participant reported discontinuation/removal of their implant	Proportion of participants who report removal of the implant and time to this event.
Participant reported EQ-5D-5L and ICECAP-A	Derived according to published scoring systems.

Participant reported treatment and healthcare usage	Participant Questionnaire
Intention to continue of their allocated treatment after unblinding	Participant Questionnaire

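### Implant removal is a questionnaire outcome at days 30, 60 and 90 with time to event, but the 90-day questionnaire list asks only about intention to continue

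*Protocol*

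**What the plan says.** The Trial Summary names "Discontinuation of allocated treatment and of implant" as a secondary outcome under safety. Table 2 (section 2.3) carries the implant part as "Participant reported discontinuation/removal of their implant", collected by participant questionnaire at days 30, 60 and 90. Table 10 (section 14.2.2) defines the derived measure as "Proportion of participants who report removal of the implant and time to this event".

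The questionnaire contents are set out in two lists. Section 8.2.10, for days 30 and 60, ends with "Removal of implant". Section 8.2.11, for day 90, repeats the other topics and adds a global impression of treatment, but has no removal entry. Its implant entry is "Intention to continue using implant and allocated trial treatment". The same section describes the end-of-trial contact: "The recruiting centre will be asked to confirm whether the participant intends to continue with their implant and allocated trial treatment".

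Table 8 covers removal that becomes known: "Any participant who notifies the trial or site team that their implant has been removed during their participation in the trial would be withdrawn" and unblinded, with no further questionnaires or diaries required and 7 days of safety follow-up. Table 7, the schedule of assessments, has no row for implant removal at any time point.

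**The concern.** The outcome tables and the data-collection section disagree about day 90. If the 90-day questionnaire follows section 8.2.11 as written, the last stretch of follow-up has no question asking whether the implant has come out, or when. Intention to continue is a different quantity: it is not a status and it carries no date.

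Three things are at stake:

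- **The secondary outcome.** The removal proportion can be too low, and the time-to-event version needs dates that nothing in the 90-day list supplies. Section 1 calls problem bleeding the most commonly reported reason for stopping the implant, so this is not a marginal measure.
- **The economic evaluation.** Section 15.3 lists implant discontinuation as a cost, and section 15.4 directs sensitivity analysis at it.
- **Interpretation of the primary rating.** Day 90 is the primary time point (section 14.2.1). A participant whose removal is known is withdrawn and owes no further questionnaires. One whose removal is not known can still give a day-90 rating, and nothing marks it as given after removal.

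**Working it through.** The point concerns data collection, so the main check sets the sections side by side.

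**1. What each place requires.**

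| Place | Day 30 | Day 60 | Day 90 |
|---|---|---|---|
| Table 2 (outcome time points) | removal | removal | removal |
| Sections 8.2.10 and 8.2.11 (questionnaire lists) | removal | removal | intention only |
| Section 8.2.11 (site contact, as regards the implant) | – | – | intention only |
| Table 7 (schedule) | no row | no row | no row |

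Tables 2 and 10 do have a separate intention outcome, but it concerns the allocated treatment. It does not stand in for removal.

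**2. Whether another route gives the missing status and date.** Table 10 needs both.

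- Spontaneous notice (Table 8) can give status, but only if the participant volunteers it.
- The day-90 item "Use of health service resources relating to problem bleeding or contraceptive use" could reveal a removal visit. It is not stated to record implant status or a removal date.
- A negative answer on intention may hint at removal. It does not separate someone who plans removal from someone who has already had it, and it gives no date.

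Each route can bring a removal to light, but none is stated to yield both facts. Late removals can therefore be missed, though not all will be.

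**3. Length of the gap.** Nominally 90 − 60 = 30 days, and 30/90 = one third of follow-up. Two features move this. The 10-day completion window in section 8.2.11 may shorten the gap for someone who answers the day-60 questionnaire late. A participant who skips the day-60 questionnaire but answers at day 90 has had no removal item since day 30: 90 − 30 = 60 days, or two thirds.

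**4. Number of events.** The protocol gives no removal rate over the trial's 90 days. The 25% early-removal figure in section 1 has no time frame. As an assumption only, if 1%, 2%, 5% or 10% of the 690 participants had a removal after the day-60 questionnaire:

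- 0.01 × 690 = 6.9, about 7
- 0.02 × 690 = 13.8, about 14
- 0.05 × 690 = 34.5, about 35
- 0.10 × 690 = 69

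These are removals without a dedicated item. The number actually missed would be lower by whatever the routes in step 2 pick up, and that share is unknown.

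**5. Sample size.** The plan's figure reproduces. With restricted proportions 0.7874 and 0.8874 under the Farrington–Manning null, s0 = √(0.7874 × 0.2126 + 0.8874 × 0.1126) = 0.517 and s1 = √(2 × 0.85 × 0.15) = 0.505. Then n = (1.960 × 0.517 + 1.282 × 0.505)² / 0.10² = 275.7 (from unrounded values), so 276 per arm, and 552/0.80 = 690. Nothing in this point changes it.

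**The case against.** The strongest reply is that section 8.2.11 lists topics and the questionnaire itself is not in the protocol. Table 2 says removal is collected at day 90, so the real form may well ask. That stands as a limit: the documents show that two sections disagree, not that no question exists. It does not remove the point, because anyone building or checking the form from section 8.2.11 would leave the item out.

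Four stronger readings are tempting, and the documents do not support them:

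- **All late removals are lost.** The indirect routes above may reveal some, and recruiting sites are themselves places that offer implant services (section 3.2).
- **Late ratings are counted as on-implant, or the primary comparison is biased.** The analysis does not classify ratings by implant status. Bias would need unnotified removals, completed day-90 ratings shifted by removal, and an imbalance between arms. None of these can be established from the protocol.
- **A specific count is missed.** One could assume 5–10% removals spread evenly over 90 days and take one third, giving 12–23 of 35–69. That rate has no source in the protocol, and the result counts all late removals rather than missed ones.
- **Participants who quietly stop their tablets go uncounted.** A reader might infer this because discontinuation of allocated treatment has no row of its own in Table 2 or Table 10. Tablet-taking is asked daily (section 8.2.9), repeated non-compliance prompts a contact (section 7.11), blister packs are returned (section 8.3.1), and the site confirms adherence where possible (section 8.2.7). Subject to diary completion, silent stopping shows in those data.

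**Conclusion.** The inconsistency is real and should be corrected. Table 2 sets a day-90 removal measurement, and section 8.2.11 lists intention instead. Followed as written, removals after the day-60 questionnaire have no dedicated item and no stated date, so the removal proportion can be understated and the time-to-removal data incomplete. A day-90 primary rating given after an unnotified removal stays in the analysis unidentified, whereas a notified removal ends the questionnaires. Participants in the same position are thus handled differently according to whether they happen to say so.

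The gap is one third of nominal follow-up. The number of removals missed cannot be given. The conclusion assumes that the 90-day questionnaire matches its list. If the form already has a dated removal item, only the text of section 8.2.11 needs correcting.

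**What to change.** Reconcile Table 2, sections 8.2.10 and 8.2.11, and Table 10:

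- Add to the 90-day questionnaire an item asking whether the implant has been removed since the last completed questionnaire (yes/no) and, if so, on what date. This wording also covers a skipped day-60 questionnaire.
- Ask for the date on the 30- and 60-day questionnaires too, so that time to removal is measured in the same way throughout.
- At the end-of-trial site contact that already takes place, record implant status and any removal date as well as intention.

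Ratings given after removal can then be identified. No extra item on stopping tablets is needed, since adherence is already tracked daily.

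The cost is one short questionnaire item and one CRF field, with slight participant burden and no extra visit.
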